### 6.3. Study design and study overview

The study design is a randomized controlled trial with serological screening and treatment as the intervention. Selected schoolchildren will be allocated into two study arms: (1) serological screening and treatment (SSAT), and (2) routine care as control arm.

At enrolment, in the SSAT arm, individuals found *P. vivax* positive by either serological (Luminex) or Giemsa stained microscopic examination regardless of the symptoms will receive supervised treatment (direct observation) with high dose PQ (daily 1 mg/kg BW) for 7 days ( $P_o=P_v$ ). In the control arm, only symptomatic individuals found *P. vivax* positive by Giemsa stained microscopic examination will receive the same regimen ( $P_o=P_v$ ). In addition, in the treated children of both arms, dihydroartemisinin-piperaquine (DHA-PP) will be given as blood schizontocide according to body weight. All other species (*P. falciparum*, *P. malariae*) found by Giemsa stained microscopic examination will be treated according to national guideline. Serological examination will be performed by Luminex (done at Eijkman, Jakarta) and point-of-care (POC) antibody detection using rapid test on site

Follow up will be performed monthly for 9 months. During this period, 400  $\mu$ L of finger pricked blood samples will be collected from all children in both arms. These samples will be tested for malaria presence by PCR which will be done at EO CRU, Jakarta. However, children with clinical symptoms (body temperature of  $\geq 37.5^\circ\text{C}$  and/or history of fever within 3 days), will be examined by Giemsa stained microscopy on site, and treated if positive (any species) according to national guideline (unsupervised).

At the last follow up, a mass blood survey will be conducted to both arms for *Pv* serological test, LMF, and PCR. Those found positive by LMF for any species will be treated regardless of their symptoms.

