### **6.7. Follow up and end of study**

First follow up will be conducted one month after the last dose of PQ treatment administration. Every visit, blood samples from finger prick and skin (LMS) will be taken. Unlike in the 16ecurrent process, malaria blood smear will be made only from participants with clinical symptoms suggestive for malaria. If positive, they will be treated. All treatment during follow up period will be provided by PHC staff according to national guideline (Appendix B table 1 & 3).

At the end of study (month-9 of the follow up), mass blood survey will be conducted to collect finger prick blood (LMF, Pv serological test, qPCR) and LMS. Seroconversion will be assessed. All LMF (+) will be treated as above.

All study subjects will be followed until the end of study (month 9) although they cannot fulfil the complete schedule.

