### **6.10. Gametocyte study**

At enrollment, blood samples will also be taken from shallow vasculature of the skin from the ankle of all participants from both arms for microscopic examination (light microscopic-skin/LMS) (figure 2). Malaria status by LMS will be assessed post-hoc and will not indicate any treatment.

To determine longevity of these skin gametocytes, LMS samples will be taken at monthly follow up. Moreover, to explore any diurnal variation of this stage, we should obtain blood samples at night and during the day. Therefore, during follow up activity, house visit will be made to the malaria infected children with symptoms for collecting two times blood samples, i.e. 7-10 AM and 7-10 PM. In addition, household members will be asked to contribute their blood samples (LMF, LMS, and PCR). For the household members, LMF will be read on site to indicate treatment.

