### **7.3. Blood smear Giemsa staining and microscopic reading**

Blood films will be dried in room temperature overnight, and fixed with methanol (thin smear only) before it is stained using 3% Giemsa made by mixing the stock solution with buffer. The stain will be gently poured into the slides until they are totally covered. After 45-60 minutes, slides will be rinsed with water and allowed to dry and read under binocular microscope with 1,000 magnification (20).

WHO certified microscopist will read the slides in the field, and cross check will be done at Jakarta. Asexual stages and gametocytes will be counted separately. For LMF, parasites will be counted against leucocytes in the thick smear. Density will be recorded as the number of parasites found per 200 leucocytes. A conversion to number of parasites in microliter of blood will be conducted under the assumption of one microliter of blood contains 8,000 leucocytes.

For LMS, parasites will be counted against RBC found in 20 HPF. Density will be recorded as number of parasites per 1 microliter. A conversion to number of parasites in microliter of blood will be conducted under the assumption of one microliter of blood contains 5,000,000 RBC.

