## APPENDIXES

### APPENDIX A. MAP OF STUDY SITE

**APPENDIX B. DRUG DOSAGE****Table 1. DHA-PP**

DHA-PP will be given for any species. Same dosage will be given at the enrollment and during follow up.

Day	Drug	Daily dosage based on body weight						
		≤ 5 kg	6-10 kg	11-17 kg	18-30 kg	31-40 kg	41-59 kg	≥ 60 kg
1-3	DHA-PP	¼	½	1	1 ½	2	3	4

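### The day and night gametocyte samples have no stated order and no stated timing relative to the first antimalarial dose, so drug clearance could pass for a diurnal difference

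*Protocol*

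**What the plan says.** The aim is in Protocol section 6.10: "to explore any diurnal variation of this stage, we should obtain blood samples at night and during the day". The means is a home visit during follow-up: "house visit will be made to the malaria infected children with symptoms for collecting two times blood samples, i.e. 7-10 AM and 7-10 PM". The background (section 4) raises a possible circadian rhythm as part of the skin-reservoir hypothesis.

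Sections 6.3 and 6.7 show how such a child is found. Section 6.7: "malaria blood smear will be made only from participants with clinical symptoms suggestive for malaria. If positive, they will be treated". Section 6.3 says that symptomatic children "will be examined by Giemsa stained microscopy on site, and treated if positive". Current fever is not required, because the symptom definition adds "and/or history of fever within 3 days". Appendix B, Table 1 gives DHA-PP for any species and states: "Same dosage will be given at the enrollment and during follow up". Table 3 adds primaquine from day 1 for *P. falciparum* and for *P. vivax*/*P. ovale*.

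Section 6.10 also asks household members for blood, with treatment guided by their own on-site slide. The family screening form in Appendix J has a night and a day entry for each family member under LMF, LMS and filter paper.

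The protocol does not say which of the two samples is taken first, whether either precedes the first dose, or whether the order is balanced across children.

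**The concern.** The finding that makes a child eligible for the paired samples also starts treatment. A comparison of one morning with one evening sample in such children can mix two things: time of day and time on drug. If most pairs run in the same order and lie after the first dose, the later sample is lower simply because parasites are clearing. A reader of the results would see a day-night contrast and could credit it to a rhythm. Recruiting more children does not help, because the bias stays the same while the standard error shrinks.

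The time to prevent this is when the samples are taken. A later analysis can adjust only for what was recorded. Of the forms in Appendix J, the follow-up form has a date per visit, the family form has only night and day labels, and the case report form has a date and tablet count per treatment day. None has an hour for a sample or a dose.

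**Working it through.** The protocol gives no sample size, power or expected difference for this comparison, so there is no stated figure to reproduce. The check asks how large a purely drug-related difference could be.

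**Inputs.** The sampling windows, 7-10 AM and 7-10 PM, come from section 6.10. The gametocyte half-life on treatment is not in the protocol; a range of 12 to 120 hours is assumed, with exponential decline.

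**Gap between the samples.**
- AM then PM: shortest 19 − 10 = 9 h, longest 22 − 7 = 15 h, midpoints 20.5 − 8.5 = 12 h.
- PM then next AM: 31 − 22 = 9 h, 34 − 19 = 15 h, midpoints 32.5 − 20.5 = 12 h.

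**Fall in the later sample, no true rhythm, both samples after the first dose.** Later/earlier ratio = 2^(−gap/half-life).

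| Assumed half-life | Ratio at 9 h | Ratio at 12 h | Ratio at 15 h | Fall at 12 h |
|---|---|---|---|---|
| 12 h | 0.59 | 0.50 | 0.42 | 50% |
| 24 h | 0.77 | 0.71 | 0.65 | 29% |
| 48 h | 0.88 | 0.84 | 0.81 | 16% |
| 120 h | 0.95 | 0.93 | 0.92 | 7% |

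If both samples precede the first dose, the drug-related fall is zero. If the dose falls between them, only the hours after it count: with 6 of the 12 hours on drug and a 24 h half-life, the fall is 1 − 2^(−6/24) = 16% instead of 29%.

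**Effect of order.** Let q be the share of children sampled AM first. With a 12 h gap, the PM/AM geometric mean ratio from clearance alone is 2^(−(2q−1)·12/half-life).

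| Share AM first | Half-life 12 h | 24 h | 48 h |
|---|---|---|---|
| 1.00 | 0.50 | 0.71 | 0.84 |
| 0.75 | 0.71 | 0.84 | 0.92 |
| 0.50 | 1.00 | 1.00 | 1.00 |
| 0.25 | 1.41 | 1.19 | 1.09 |
| 0.00 | 2.00 | 1.41 | 1.19 |

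The artefact can therefore take either sign, and it averages out when order is balanced. Exact cancellation needs the same proportional decline in both orders.

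**Chance of a falsely significant contrast.** Assume a fixed order, 20 children, a within-child SD of 1.0 for the difference in log density, and a two-sided 5% test. With d = ln 2 × 12/half-life, the probability is Φ(d√20 − 1.96) + Φ(−d√20 − 1.96). This gives 0.87, 0.34, 0.12 and 0.06 for half-lives of 12, 24, 48 and 120 h. With 40 children it is 0.99, 0.59, 0.19 and 0.07. The number of children and the SD are illustrations; the protocol gives neither.

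**The case against.** Three stronger readings are tempting, and the protocol supports none of them.

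- *Only febrile, treated children give day and night samples.* A fever history within 3 days is enough, and the family form has night and day entries for household members. Members with a negative slide are not treated under the protocol and could serve as an untreated comparison, though few may carry gametocytes.
- *The later sample is always about 12 hours further on drug.* Nothing ties the first dose to the house visits. Section 7.3 says "Blood films will be dried in room temperature overnight", whereas the synopsis, for enrolment, has slides read straight after collection. These statements need reconciling, and they leave the start of treatment unclear. Both samples could precede it.
- *Evening comes first, so the morning count is lowered.* The family form prints night above day, but section 6.10 names the morning window first. Neither is a visit schedule.

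The objector can add that clearance may be slow. Section 4 hypothesises long residence in the skin, and at 120 h the fall is 7% and the false-positive chance close to nominal. The question is also exploratory: it is not among the endpoints in section 5, and section 8.3 has no day-night analysis. Visit order and adjustment might be set in an operating procedure or the SAP.

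Most of this stands and limits the point. It does not remove it. Section 6.10 fixes the two windows and the eligible children but leaves order open, and the case report form recovers the day of the first dose but not the hour. An adjustment written later cannot use times that the forms never captured.

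**Conclusion.** The point holds as a narrow design weakness. The morning-evening contrast in treated children is open to confounding with drug clearance, because sample order is neither fixed nor balanced, neither sample is placed relative to the first dose, and the forms shown lack the times needed to separate the two effects.

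Its size depends on two things that the protocol does not give: how uneven the order turns out to be, and how fast gametocytes decline on treatment. In the worst case (one order throughout, both samples on drug) the spurious difference runs from large to negligible over the assumed half-lives. With mixed order, or samples taken before the first dose, it shrinks or disappears. The direction cannot be predicted. The primary endpoint and all listed secondary endpoints are untouched, so the priority is low.

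**What to change.** In section 6.10 and the matching forms:

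1. Alternate or randomise which sample comes first, from a prepared list.
2. Record the clock time of each sample and of the first antimalarial dose. Follow-up treatment is unsupervised, so the dose hour may rest on the family's report.
3. Compare AM with PM within child, adjusting for sample order or hours since first dose.
4. Analyse treated participants separately from the slide-negative, untreated household members who also give night and day samples.

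When treatment is given does not change.

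The cost is an order list and two added time fields. The scientific downside is that some pairs will start later after the positive slide, when fewer gametocytes may be detectable. The protocol gives no expected number of pairs, so adjustment may be imprecise. Balancing the order protects the average contrast even then, provided the decline is similar in both orders.

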**Figure 2. Location of ankle blood sampling**

### 6.11. Other substudies

During enrollment, several diagnostic tests will be performed to all schoolchildren as substudies: magneto-optical detection of hemozoin/MOD (finger prick and skin), hemoglobinopathy screening by HemeChip (finger prick), and Hb Sahli.

### 6.12. Ethical clearance

The study protocol will be submitted to Ethic Committee Faculty of Medicine, University of Indonesia, the Oxford Tropical Diseases Research Ethics Committee (OXTREC), and Walter and Eliza Hall Institute Human Research Ethics Committee to obtain ethical clearance. Upon above approval, the protocol will be sent to the local government of Malaka regency to obtain the local permit.

## **7. Laboratory Methods**

### **7.1. Blood Collection and Transportation**

#### **7.1.1. Finger-prick Blood Sample Collection**

Blood samples will be drawn from fingertip using BD lancet. During enrolment, malaria blood smear, POC rapid *Pv* antibody detection, hemozoin detection, and hemoglobinopathy screening will be done directly on site. Then 400 µL blood will be collected into microtainer tube containing EDTA. The microtainer tubes will be placed into the ice box, and delivered in no more than 4 hours to the field laboratory for further process.

During follow up (month 1-month 8), only 400 µL of finger pricked blood will be collected into the microtainer. At month-9, malaria blood smear and POC *Pv* antibody detection will again be done on site, as an addition to the 400 µL microtainer blood.

#### **7.1.2. Skin Blood Samples**

To collect blood from skin of the ankle, a vacuum-assisted lancet (Genteel®) will be used with penetration depth of 600 µm. The selected location is shown in the Figure 2. An alternative site will be dorsal surface of the foot between second and middle toe. Thin blood smear will be done directly from the skin blood using microcapillary tube or micropipette. This almost completely painless procedure may repeated one or more times (up to 3 times) to sufficient blood volume.

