this species. However, a typical anopheline has a proboscis about 300 microns in length, in which its protrudable feeding parts are housed. Its feeding depth would certainly not exceed that reach and would probably be considerably shorter. Gametocytes must be near to the surface of the skin in order to infect anopheline mosquitoes (i.e., survive to reproduce). We know that microscopically sub-patent volunteers very often infect anophelines allowed to feed on their skin while being 5-times less likely to infect anophelines simultaneously allowed to membrane feed on a sample of venous blood (4). Other studies have reported very similar findings (5). Those studies corroborate earlier reports of sexual stage gametocytes in skin vasculature occurring at 3-fold higher numbers relative to peripheral blood (finger stick) (6). We hypothesize that gametocytes observed in finger stick samples of vasculature well below 300 microns (typically about 600 microns) rapidly transit that compartment on their way to longer-term sequestration in the microvasculature of the uppermost dermis, just below the epidermis. That is precisely where they need to be, and a protracted residence in that compartment may explain their virtually dormant metabolic state (7), much like that of latent hypnozoites in hepatic cells (8). Human hosts experiencing exceptional and fleeting states of infection like symptomatic patency may go on to host silent, stable, and durable infections of the shallow skin microvasculature by sexual plasmodia. Moreover, these sexual stage should be distributed in such a way to increase the odds of being taken up by the mosquito, i.e. feet and ankle, where anopheles shows the strong preference (9). There is also possibility they have circadian rhythm (10).

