**APPENDIX G. PENETRATION DEPTH OF GENTEEL® LANCING DEVICE**

Contact Tip Color	Penetration Depth in mm
Blue	0.025
Yellow	0.66
Green	1.30
Clear	2.00
Orange	2.57
Violet	3.20

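### The ankle (LMS) sample called shallow is taken at 600 microns, twice the depth of the hypothesised skin reservoir, so an LMS–LMF difference cannot be attributed to depth

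*Protocol*

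**What the plan says.** Protocol section 4 builds the skin hypothesis on depth. It notes that "a typical anopheline has a proboscis about 300 microns in length" and adds: "Its feeding depth would certainly not exceed that reach and would probably be considerably shorter". It then contrasts two compartments. The first holds gametocytes that are only passing through, namely those from "finger stick samples of vasculature well below 300 microns (typically about 600 microns) rapidly transit that compartment". The second, given as the place where they persist, is described by the phrase "longer-term sequestration in the microvasculature of the uppermost dermis, just below the epidermis". The same paragraph adds a second idea, about body site: sexual stages should be concentrated at the feet and ankles, where the vector prefers to bite.

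Endpoint VIII (synopsis and section 5.2) and section 6.10 describe the ankle sample as coming from shallow skin vasculature. Section 7.1.2 fixes how it is obtained: "a vacuum-assisted lancet (Genteel®) will be used with penetration depth of 600" microns, with blood going to a thin smear. Appendix G, under the column "Penetration Depth in mm", lists six tips: 0.025, 0.66, 1.30, 2.00, 2.57 and 3.20.

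For the finger sample, section 7.1.1 names a BD lancet and gives no depth. Section 7.3 counts LMF parasites on a thick smear against leucocytes, and LMS parasites against red cells.

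Two places draw on the depth idea for interpretation. Section 4 offers hemozoin detection at the ankle or foot as further evidence for the skin reservoir. Section 10 looks ahead to what gametocytes sequestered in the upper dermis would mean for the field.

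**The concern.** A sample meant to represent a shallow compartment should either come mainly from that compartment or differ in depth from its comparator in a known way. On the protocol's figures the ankle sample does neither. It reaches well past the layer where the reservoir is placed, to the depth that the rationale assigns to the compartment that gametocytes only pass through.

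What is at stake is interpretation, not estimation. If LMS finds more gametocytes than LMF, or finds them for longer, a reader of section 4 would be inclined to credit the upper dermis. If LMS finds no more, the same reader might count that against the reservoir. The sampling supports neither step securely. Appendix G adds a practical problem, because the stated depth does not correspond to any listed tip.

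**Working it through.** No sample size, power or error rate depends on this point. The check compares depths in a single unit and then lists what differs between the two samples.

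**Inputs**
- Mosquito reach, used to locate the shallow compartment: about 300 microns (section 4).
- Typical finger-stick vasculature: about 600 microns (section 4).
- Ankle lancet: 600 microns (section 7.1.2).
- Appendix G tips: 25, 660, 1300, 2000, 2570 and 3200 microns, converted from mm.
- Trial finger lancet: depth not stated (section 7.1.1).

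**Depth comparisons**
1. Ankle depth relative to mosquito reach: 600/300 = 2.0.
2. Ankle depth minus typical finger-stick depth: 600 − 600 = 0 microns. The only finger-stick depth in the document gives no depth contrast.
3. Nearest Appendix G tip to 600 microns: 660. The gap is 660 − 600 = 60 microns, and 660/600 = 1.1, so this tip is 10% deeper than stated. Relative to mosquito reach, 660/300 = 2.2.
4. Appendix G tips under 300 microns: one of six (25 microns). None lies between 25 and 660 microns.

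**What differs between LMS and LMF**

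| Feature | LMS | LMF |
|---|---|---|
| Site | ankle (or dorsum of foot) | fingertip |
| Device | vacuum-assisted Genteel | BD lancet |
| Depth | 600 microns as stated; no such tip listed | not stated; about 600 microns typical |
| Smear and count | thin, against red cells | thick, against leucocytes |

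Site, device and smear type all change together. Depth may or may not change, and the document does not allow a reader to tell. The McNemar comparison of LMF with LMS in section 8.3 will show whether the two methods disagree. It cannot show which of these features is responsible.

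**The case against.** The strongest reply is that no objective or endpoint tests depth. Synopsis objectives IV and V ask for the accuracy of ankle microscopy against finger microscopy and PCR, and for gametocyte duration in ankle and finger blood. The section 8.3 analyses (two-by-two tables against qPCR, McNemar, half-life) can be carried out at any lancet depth. This stands, and those objectives need no rewording.

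The reply also holds against several stronger readings that a reader might infer:

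- *That LMS cannot inform the skin hypothesis at all.* Section 4 also predicts concentration at the feet and ankles, and an ankle–finger difference bears on that. A 600-micron puncture also crosses the top 300 microns, so the blood is a mixture. Mixing dilutes a shallow signal without necessarily removing it, and no mixing fraction is given. By the same logic a finger stick also contains some shallow blood.
- *That LMS and LMF are known to be drawn at the same depth.* The 600 microns for finger sticks is a general background figure. If the BD lancet goes deeper, some contrast exists.
- *That the plan breaches a 300-micron sampling limit.* Section 4 gives 300 microns as proboscis length and as a bound on feeding depth. It is not a sampling specification.
- *That section 10 commits to reporting an upper-dermis finding.* Its wording is conditional and describes possible applications.

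The gap between 600 and 660 microns could be simple rounding to the 0.66 mm tip. That is plausible, but the document does not say so.

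What remains is that the sample labelled shallow is not confined to the shallow compartment as section 4 describes it, and that depth cannot be separated from the other differences.

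**Conclusion.** The point holds as one of labelling, specification and interpretation in a secondary substudy. The stated ankle depth is 2.0 times the mosquito reach that section 4 uses to locate the reservoir (2.2 times if the 0.66 mm tip is meant). It matches the only finger-stick depth given, and it corresponds to no tip in Appendix G. An LMS–LMF difference therefore cannot be attributed to depth, and an upper-dermis reading of the ankle microscopy or the skin hemozoin result is not supported. Accuracy and gametocyte duration for ankle blood as collected remain estimable, and the body-site question remains open to study.

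This rests on taking section 4's approximate depths at face value. A deeper finger lancet would create some depth contrast, but the ankle puncture would still extend to twice the stated reach, and site, device and smear type would still differ. An analysis plan could not repair this, because depth of origin cannot be recovered from the smears. The primary endpoint and the sample size are untouched, and section 6.10 states that LMS results do not determine treatment.

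**What to change.** 1. Reconcile section 4, section 6.10, section 7.1.2 and Appendix G on the depth of the ankle sample.
2. In section 7.1.2, state the depth of the Appendix G tip actually used. In section 7.1.1, state the depth of the finger lancet.
3. In endpoint VIII (synopsis and section 5.2) and section 6.10, describe LMS as ankle capillary blood at that depth, in place of the shallow-vasculature label.
4. In the hemozoin paragraph of section 4 and in section 10, limit the interpretation to ankle versus finger blood, with no conclusion about the upper dermis.

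Objectives IV and V stay as they are. Recording the tip colour for each sample is needed only if more than one tip is used.

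The cost is a few lines of protocol text and a narrower claim for a secondary substudy. No additional sampling or analysis is required.
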